4.1. Determination of Sample Size

Sample sizes were estimated for this open-label study using within-subject change as the measure of improvement. Given the limited data from interventional trials in these patient populations, and that this is the first clinical study of NNZ-2591 IMP in this population, treatment change estimates were based on Clinical Global Impression Scale of Improvement (CGI-I) data from completed clinical trials in other rare, neurodevelopmental disorders. Based on the information provided in Glaze et al. 2019 (Double-blind, randomized, placebo-controlled study of trofinetide in pediatric Rett syndrome), the standard deviation of the CGI-I is approximately 0.7 at a single timepoint. For a sample size of 20 subjects, a two-sided significance level of 0.05, and a Wilcoxon signed-rank test, the study will be able to detect a difference of 0.55 units of change in the CGI-I at a power of 0.90. For a power of 0.80, 0.85, and 0.90, the detectable difference would be 0.48, 0.51, and 0.55 or larger, respectively. The effect size for a power of 0.80, 0.85, and 0.90 is 0.68, 0.73, and 0.79, respectively. If the observed standard deviation is larger, the size of the detectable difference would also be larger. For example, if the standard deviation is 1.45, the detectable difference for a power of 0.80, 0.85, and 0.90 is 1.02, 1.09, and 1.18 or larger, respectively.

4.2. Handling of Dropouts or Missing Data

4.2.1. Missing Dates

For incomplete dates related to adverse events, concomitant medications, or medical history, the dates will be imputed as follows:

If the incomplete date is a start/onset date:

(1) if the month and year are present, then the first day of the month will be used for day.

(2) if only the year is present, then the first day of January will be used for month and day.

If the incomplete date is an end date:

- (1) if the month and year are present, then the last day of the month will be used for day.
- (2) if only the year is present, then the last day of December will be used for month and day. If the reported year is the same as the informed consent year, then the informed consent date will be used.

If the date of last dose is missing, then it will be imputed to the subject participation end date.

Dates that are completely missing will not be imputed.

Dates related to efficacy measures will not be imputed.

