9. STUDY PROCEDURES

9.1 Overview of Study Visits

There are a total of 17 study visits over the duration of the study: 5 in-clinic visits and 12 remote/in-home visits (6 combined telemedicine/in-home nursing visits, and 6 in-home nurse visits; refer to the table of assessments in Section 4). Remote visits between the Investigator or designee at the clinical site and the subject at home are conducted via telemedicine or video facilities as appropriate. In-home visit refers to a visit made to the subject's home by a visiting nurse.

The Screening/Baseline period will be conducted over 4 to 6 weeks. The second visit during the Screening/Baseline period (Visit 2) should be conducted 2 weeks ± 1 day after the Screening visit (Visit 1). The subject will then remain in Screening for an additional 2 to 4 weeks. The caregiver diary must be completed daily during the entire Screening/Baseline period whether it is 4 weeks or 6 weeks. The Screening visit (Visit 1) and Baseline visit (Visit 3) may be conducted over three consecutive days. It is preferrable that ECGs, safety labs and biomarker sample collection are conducted on the same day. No assessments can be conducted until informed consent has been given by the caregiver or legally authorized representative. Also, training for the caregivers on all caregiver completed assessments must be done before the caregiver rater may complete the assessments. All assessments must be done within the window for the visit, as shown in the Schedule of Assessments in Section 4. For Visit 3, all assessments must be done before administration of the IMP.

The in-clinic visits will be conducted in person at the study site. As described below, safety and efficacy assessments will be completed by site personnel. The caregiver will also complete caregiver assessments the day of the visit or the day before the visit as described below (except the caregiver diary which is completed daily), and these will be reviewed by site personnel. In-clinic visits will be done at Screening (Visit 1), Baseline (Visit 3), Week 2 (Visit 5), Week 6 (Visit 9), and Week 13 (EOT, Visit 16). For all visits designated as in-clinic (Visits 1, 3, 5, 9 and 16), an in-person visit is preferred. Off-site assessments may be allowed due to extenuating circumstances such as the COVID-19 health emergency. All requests for off-site assessments must be approved in advance by the Sponsor or Medical Monitor.

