9.3 Screening and Baseline Procedures

Screening and Baseline assessments are completed after informed consent during a period of approximately 4 to 6 weeks. During the Screening/Baseline period data will also be collected to establish the subject's baseline characteristics and symptom severity based on assessments collected during the 4 to 6 week period. There are two in-clinic visits and one remote/in-home visit for Screening and Baseline: Screening (Visit 1, in-clinic), Screening Visit 2, (combined remote/in-home nurse visit), Baseline (Visit 3, In-clinic). The second visit during the Screening period (Visit 2) should be conducted 2 weeks \pm 1 day after the Screening visit (Visit 1). The subject will then remain in Screening for an additional 2 to 4 weeks. The caregiver diary must be completed daily during the entire Screening period whether it is 4 weeks or 6 weeks.

During the Screening visit (Visit 1), informed consent to participate in the study will be obtained from the parent or legally authorized representative.

Subjects will be evaluated for the diagnosis of PMS and documented disease-causing genetic abnormality of *SHANK3*. If the subject has been genotyped at any time in the past, these will not need to be repeated at Screening, provided the documentation of these tests is available for verification.

A rapid screening test for SARS-CoV-2 will be conducted by the site at Screening and Baseline. At Screening, a complete medical history will be conducted, and a neurological and physician exam will be done.

Caregivers will complete a 4 to 6 week diary to record seizure frequency, urine frequency (number of voids), any changes in symptoms or oral intake, and any changes in concomitant medications.

Baseline cognitive characteristics will be assessed at the Screening visit using the Stanford-Binet Intelligence Scales version 5 (SB5) scored using the z-deviation method for intellectual disability or the Mullen Scales of Early Learning (Mullen) developmental quotients⁵⁰. The Mullen will be done for subjects who cannot achieve basal on the SB5 or for whom the SB5 is developmentally inappropriate.

Neuren Pharmaceuticals Ltd.	Clinical Trial Protocol	Version 3.0
Confidential	Neu-2591-PMS-001	October 30, 2023

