10.1 Definition of Adverse Event

An adverse event is any untoward medical occurrence associated with the use of a drug in humans, whether or not considered drug related. An AE can be any unfavorable and unintended sign (e.g., an abnormal laboratory finding), symptom or disease temporally associated with the use of a drug, without any judgment about causality.

AEs can include the following:

- Exacerbation of a chronic or intermittent pre-existing condition including either an increase in frequency and/or intensity of the condition.
- Conditions detected or diagnosed after IMP administration even though it may have been present prior to the start of the study.
- Signs, symptoms, or the clinical sequelae of a suspected interaction.
- Signs, symptoms, or the clinical sequelae of a suspected overdose of either IMP or a concurrent medication.

SAEs are a sub-category of AEs that are defined in Section 10.2, below. AEs/SAEs are recorded and reported from the time of first dose of IMP until Follow-up (Visit 17).

Planned hospital admissions for an illness or a disease that existed prior to administration of IMP or enrollment at the clinical study are not to be considered AEs. Individuals who have planned surgical procedures that would occur during the study are to be excluded from the study (Exclusion 43). If the subject has a planned hospital admission (non-surgical), the Investigator should consult with the Medical Monitor to ensure this will not cause disruption of IP administration or would not qualify the subject for exclusion.

Note that medical or surgical procedures are not considered AEs (e.g., endoscopy); however the condition that leads to the procedure is an AE.

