6.2. Adverse Events

Adverse events summaries will only consider treatment emergent adverse events (TEAEs). TEAEs are defined as those adverse events that occurred after dosing and those existing adverse events that worsened during the study based on the start date and time. If it cannot be determined whether the adverse event is treatment emergent due to an incomplete (partial) onset date, the adverse event will be considered treatment emergent. AEs will be recorded from the time of first dose of IMP until Follow-up (Visit 17).

Verbatim terms entered into the clinical database via the EDC system will be mapped to preferred terms and system organ classes using version 25.1 of Medical Dictionary for Regulatory Activities (MedDRA).

Summaries that are displayed by system organ class and preferred terms will be ordered by descending order of incidence of system organ class and preferred term within each system organ class. Adverse event summaries of the following types will be presented for the Safety Population:

- Overall summary of the TEAEs which contain an overview of each item below.
- Subject count and incidence rate of TEAEs and total number of unique TEAEs by MedDRA system organ class and preferred term.
- Incidence rate of TEAEs by MedDRA preferred term and highest severity. Severity is defined by three categories: "Mild", "Moderate", and "Severe." At each level of subject summarization, a subject is classified according to the highest severity if the subject reported one or more events. Adverse events with missing severity will be considered severe for this summary.
- Subject count and incidence rate of TEAEs by MedDRA preferred term and
 closest relationship to study drug (Related/Not Related). At each level of subject
 summarization, a subject is classified according to the closest relationship if the
 subject reported one or more events. Adverse events with missing relationship
 will be considered related for this summary.
- Subject count and incidence rate of Serious TEAEs by MedDRA system organ class and preferred term.
- Subject count and incidence rate of TEAEs leading to withdrawal of study medication by MedDRA system organ class and preferred term.
- Subject count and incidence rate of TEAEs leading to dose modification (defined as dose increased, dose reduced, dose interrupted on the CRF) by MedDRA system organ class and preferred term.

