6.8. Prior and Concomitant Medications

Prior and concomitant medication verbatim terms captured via the EDC system will be mapped to Anatomical/Therapeutic/Chemical (ATC) class and Preferred Names using the September 1, 2022 version of the World Health Organization (WHO) Drug Dictionary Enhanced available.

Prior and concomitant medications will be summarized separately by WHO ATC class and preferred name. Medications with an end date prior to first dose will be considered prior medications. Medications that are taken during while on study medication will be considered concomitant medications. These summaries will present the number and percent of subjects using each medication. Subjects may have more than one medication per ATC class and preferred name. At each level of subject summarization, a subject is counted once if one or more medications at that level is reported for the subject. Each summary will be ordered by descending order of incidence of ATC class and preferred term.

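### The SAP's consent-date rule for year-only end dates places the end of on-treatment adverse events and drug stops before the first dose

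*SAP*

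**What the plan says.** SAP 4.2.1 gives a single rule for three kinds of record: "For incomplete dates related to adverse events, concomitant medications, or medical history, the dates will be imputed as follows". Under end dates, the second item starts with a default, "if only the year is present, then the last day of December will be used for month and day", and then overrides it: "If the reported year is the same as the informed consent year, then the informed consent date will be used". The override is not limited to any record type. Nothing in the section stops an imputed end date from falling before the record's start date or before first dose. Dates that are wholly missing are left missing.

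The timing comes from the protocol. Section 9.3 states: "During the Screening visit (Visit 1), informed consent to participate in the study will be obtained from the parent or legally authorized representative". Section 9.1 adds: "The Screening/Baseline period will be conducted over 4 to 6 weeks". First dose follows at or just after Visit 3.

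Both documents start adverse event recording at first dose (SAP 6.2; protocol 10.1: "AEs/SAEs are recorded and reported from the time of first dose of IMP until Follow-up (Visit 17"). SAP 6.8 says of medications: "Medications with an end date prior to first dose will be considered prior medications". Its next sentence classes drugs taken while on study medication as concomitant.

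**The concern.** The consent date is a sensible upper limit for something that finished before the study. It is not a possible end date for something that can only begin after dosing starts. Because the override sits in the common rule, it applies to both kinds of record.

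Three outputs are exposed:

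- the adverse event listings, and any duration derived from them;
- the split between the prior and concomitant medication tables;
- the on-treatment medication count (SAP 4.3), which sets the above-6 versus 6-or-fewer colour coding of the efficacy plots (SAP 8.1.2).

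Program validation would not catch the error, because SAP section 4 checks programs for consistency with the plan. A faithful program would reproduce it.

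**Working it through.** The plan gives no figure to reproduce, so the check is date arithmetic on the rule as written.

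**Inputs.** C = consent date (Visit 1). G = days from consent to first dose. s = days from first dose to the true onset or drug stop. The longest s for an adverse event is 108: 90 days from Day 1 to Day 91, plus 14 days to Week 15, plus the 4-day window.

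**Gap.** Nominally G runs from 4 × 7 = 28 to 6 × 7 = 42 days. If the ±2-day windows at Visits 1 and 3 are both used, and first dose may fall on the day after Visit 3, G runs from 28 − 2 − 2 = 24 to 42 + 2 + 2 + 1 = 47. Adding the windows in this way is my assumption.

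**Adverse events with a complete onset date.** Onset = C + G + s and imputed end = C, so end minus onset = −(G + s), which is always negative. The shortfall runs from 28 to 42 + 108 = 150 days nominally, and from 24 to 47 + 108 = 155 days with windows. An enumeration over 365 consent dates, every G in range, and s from 0 to 108 in 6-day steps, keeping only events that ended in the consent year, agrees:

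| Case | Reached by the override | Imputed end before onset |
|---|---|---|
| Nominal gap | 78,660 of 365 × 15 × 19 = 104,025 (76%) | 78,660 of 78,660 |
| With windows | 125,628 of 365 × 24 × 19 = 166,440 (75%) | 125,628 of 125,628 |

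**Drugs stopped on treatment.** Imputed end = C, which is before first dose, C + G. With s from 0 to 90 in 6-day steps:

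| Case | Reached by the override | Imputed end before first dose |
|---|---|---|
| Nominal gap | 68,400 of 365 × 15 × 16 = 87,600 (78%) | 68,400 of 68,400 |
| With windows | 109,248 of 365 × 24 × 16 = 140,160 (78%) | 109,248 of 109,248 |

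The 75% to 78% shares assume consent dates spread evenly over a year, which the documents do not state. They describe how often an on-study end falls in the consent year. They do not say how often an end date is known only to the year.

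**Example.** Consent is on 1 September 2022, first dose on 29 September (28 days later) and Day 91 on 28 December. An adverse event or drug stop recorded as ending in 2022 is given an end date of 1 September, 28 days before first dose.

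**Partial onset dates.** The same section sets a year-only onset to 1 January. The consent date cannot precede that, so the duration is not negative. In the example, an onset recorded as September 2022 becomes 1 September, so start and end coincide. In both cases the imputed end still lies before dosing.

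**A drug stopped before consent.** Suppose, in the same example, a drug stopped in March 2022 and only the year was recorded. The override gives 1 September, before first dose, and the drug is correctly prior. Without the override it would take 31 December or the capped study end. Both fall after 29 September, so the drug would no longer meet the prior definition.

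**After the change.** For on-treatment records, 31 December capped at the end of participation gives no adverse event ending before onset (0 of 78,660; 0 of 125,628 with windows). It gives no drug stop before first dose (0 of 68,400; 0 of 109,248).

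**The case against.** The strongest reply is that the rule rarely applies and seldom affects a result. Most of this stands.

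- **Planned adverse event tables.** A reader might infer that the safety tables would be wrong. The documents do not support that. SAP 6.2 determines treatment-emergent status from the start date, and none of its listed summaries uses an end date or a duration.
- **Negative durations.** A reader might infer that every affected adverse event has a negative duration. That holds only when the onset date is complete, or partial but later than consent after imputation.
- **Continuing drugs.** A reader might infer that every drug carried into treatment becomes prior. An ongoing drug has no end date, and a wholly missing date is not imputed. Only a stop in the consent year with the month unknown is reached.
- **Certain reclassification.** The second definition in SAP 6.8 and the count in SAP 4.3 both turn on use during treatment. A drug known to have been taken then can still be classed as concomitant. Reclassification is possible, not certain, because the SAP does not say which definition prevails.
- **Frequency.** Medication changes and symptoms are logged in a daily caregiver diary that is reviewed at every visit (protocol 9.5.10). An on-study stop known only to the year should be unusual.
- **Use of the count.** It excludes as-needed drugs, it only colours plots, and SAP 7.3 plans no subgroup analyses.
- **Pre-study records.** The override works for drugs stopped before consent. The protocol's look-back periods for earlier treatments make such records plausible, so deleting the sentence outright would create the opposite error.

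None of this makes the consent date a possible end date for an adverse event or an on-treatment drug stop.

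**Conclusion.** The rule is wrong as written for two kinds of record. Every adverse event it reaches gets an end date before dosing, and before its own onset when that date is complete, by at least 28 days nominally or 24 with windows. Every on-treatment drug stop it reaches gets a pre-dose end date and satisfies the prior definition, while possibly satisfying the concomitant one as well.

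The practical impact is small. Adverse event incidence is unaffected, and no test depends on these dates. What can change is listings and any derived durations, the placement of a few drugs between two tables, and possibly a subject's colour group in the plots.

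This rests on consent being taken at Visit 1, on adverse events being recorded only from first dose, and on the override being applied literally to all three record types. The number of year-only end dates is not given in the documents. I have assumed that it is low.

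**What to change.** In SAP 4.2.1, limit the consent-date sentence to medical history and medication records marked as having ended before consent. For adverse events, and for medications started on or after first dose or known to have been taken on treatment, impute a year-only end date as the earlier of 31 December and the subject's participation end date, and never earlier than the recorded or imputed start date.

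In SAP 6.8, state that known on-treatment use takes precedence over an imputed end date.

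A medication started before first dose, with a year-only end and no indication of whether it stopped before consent, fits neither group. Sites should be queried on these records.

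The cost is two or three sentences and a few lines of derivation code, with no new data collection beyond those queries. Make the change before database lock, since SAP section 4 labels analyses added after lock as post hoc.

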4.2.2. Baseline Values

Baseline values that are missing will not be imputed for safety or efficacy measures. For assessments collected at more than one visit during the Screening/Baseline period,the baseline measurement for an efficacy variable will be based on the average all non-missing values from visits 1-3.

4.2.3. Post-baseline Values

For subjects who discontinue the study, data will be analyzed up to the last observation for safety and efficacy measures. Missing data for safety assessments will not be imputed. For efficacy measures, if an assessment has been completed but has missing items, missing values shall be imputed as follows:

- If 3 or fewer items are missing, the last observation for that particular data element (e.g., item response) will be carried forward.
- The scoring algorithms will be applied including the observed values and last observation carried forward (LOCF) for the missing items
- These rules will only apply to individual items. Total scores, subdomain and subscale scores will not be carried forward. If the assessment is completely missing, items will not be imputed.

4.3. Definitions

- The baseline measurement for an efficacy variable will be based on the average values of visits 1-3 for assessments collected at more than one visit. For assessments collected once during the Screening/Baseline period, the most recent non-missing assessment will be used. For safety assessments, value at Visit 3 (Baseline) or the most recent non-missing assessment will be used.
- Age will be derived as the integer value of informed consent/assent date minus birth date plus one, then divided by 365.25.
- The age at time of assessment in calculated as (date of assessment date of birth + 1)/365.25.
- Body Mass Index (BMI) will be derived as weight in kilograms divided by height in meters squared.
- The change from baseline measurement for a variable at a particular visit will be derived as the measurement taken at the specified visit minus the baseline measurement. CGI-I will not have a change from baseline measurement; the within-subject treatment change is assessed by the value at the End of Treatment Visit.
- Treatment duration in days will be derived as follows: Date of Last Dose Date of First Dose + 1.
- Study duration will be defined as the total number of days in the study (date of last visit date of informed consent + 1).
- History of developmental regression will be determined from the medical history question as reported on the PMS diagnosis page of the CRF: "Has the child undergone a regression of skills in the past?" If coded as "yes" the subject is considered as having had a past developmental regression.
- Autism Spectrum Disorder (ASD) diagnosis will be derived from the PMS diagnosis page of the CRF. If ASD is checked to the under "confirmation of psychiatric co-morbidities", the subject is considered as having the disorder-
- Bipolar Disorder will be derived from the PMS diagnosis page on the Case Report Form (CRF). If "Bipolar disorders" is checked to the under "confirmation of psychiatric co-morbidities", the subject is considered as having the disorder.

- Attention Deficit Disorder will be derived from the PMS diagnosis page on the CRF. If "Attention Deficit Disorder" is checked to the under "confirmation of psychiatric co-morbidities", the subject is considered as having the disorder.
- Obsessive-compulsive Disorder will be derived from the PMS diagnosis page on the CRF. If "Obsessive-compulsive disorder" is checked to the under "confirmation of psychiatric co-morbidities", the subject is considered as having the disorder.
- Dose modification is defined as dose increased, dose reduced, or dose interrupted responses for the action taken with study treatment on the adverse event (AE) CRF.
- Improvement in the top 3 concerns will be derived as a decrease in severity (change from baseline <0).
- Baseline seizure frequency will be determined based on the number of seizures recorded in the diary during the 4–6-week screening period. The baseline monthly seizure frequency will be derived by dividing the total number of seizures during the screening/baseline period by the screening/baseline duration in months ([first dose date screening date] divided by 30.4375). The baseline weekly seizure frequency will be derived by dividing the total number of seizures during the screening/baseline period by the screening/baseline duration in weeks ([first dose date screening date] divided by 7). During the treatment period (Visits 4 16), the seizure frequency will be derived by summing the number of seizures recorded in the diary over treatment. The monthly seizure frequency will be derived by dividing the total number of seizures during the treatment period by the treatment duration in months (treatment duration divided by 30.4375). The weekly seizure frequency will be derived by dividing the total number of seizures during the treatment period by the treatment duration in weeks (treatment duration ([first dose date screening date] divided by 7).
- The Mullen Scales of Early Learning developmental quotient (DQ) is calculated as the (mean of the age equivalent in months of the corresponding scales/chronological age in months) x 100. For the overall DQ, the mean of the fine motor, receptive language, expressive language, visual reception is included. For the non-verbal DQ, the mean of the fine motor and visual reception scales are included. For the verbal DQ, the receptive language and expressive language scales are included.
- For the Mullens Scales of Early Learning and the Stanford-Binet 5, Chronological age in months will be calculated as (date of assessment date of birth + 1)/30.4375.

• The number of concomitant medications will be summed across subjects for all unique medications that are taken while on treatment. Medications taken with a frequency of PRN or "as needed" will be excluded from the count.

5. Subject Information

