9.5.10 Caregiver Diary

A Caregiver Diary will be completed daily by the caregiver and reviewed at all visits by the Investigator and by the visiting nurse at remote visits. In the diary, the subject's caregiver will record dosing compliance of IMP, any changes in concomitant medication or treatments, urine output measured by number of voids or wet diapers, any changes in symptoms including changes in oral intake and seizure activity. The diary also specifically queries changes in maladaptive behavior or self-injury which may suggest changes in the tendency to self-harm. At the Screening visit, the clinician will review the assessment with the caregiver and assist the caregiver to define the child's typical seizure types or other chronic conditions that are to be tracked in the diary. Any new, emergent types of seizures or new symptoms will also be documented if they occur.

The Investigator must review the caregiver diary at or after each visit. At clinic visits, the Investigator will review the diary and the site will provide a new diary section to the caregiver. At remote visits, the nurse will review the diary in the home noting any potential issues in the nurse report and collect the diary to send to the Investigator along with notes from the visit. The nurse will provide the caregiver with a new diary section for the upcoming week. The nurse will not sign-off on the diary. The Investigator is responsible for reviewing the nurse notes, reviewing the diary, signing the diary, and determining if anything needs to be reported as an Adverse Event.

Neuren Pharmaceuticals Ltd.	Clinical Trial Protocol	Version 3.0
Confidential	Neu-2591-PMS-001	October 30, 2023

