6.9. Total, Monthly, and Weekly Seizure Episodes

Evaluation of total, monthly, and weekly seizure frequency will be derived as defined in Section 4.3. Seizure frequency will be assessed from a seizure diary that is part of the Caregiver Diary which is completed daily by the caregiver.

Summary statistics on the observed and the change from baseline in total and monthly seizures will be displayed at baseline and end of treatment. Within subject changes will be assessed using a Wilcoxon Signed Rank Test.

7. Efficacy Analysis

The secondary objective of the study is to investigate measures of efficacy during treatment with NNZ-2591 in children and adolescents with PMS.

All efficacy analyses will be conducted on the ITT population.

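### SAP 4.3 leaves the screening-period bracket in the on-treatment weekly seizure rate; secondarily, all the seizure rates divide diary counts by calendar days with no allowance for days without a diary record

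*SAP*

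**What the plan says.** SAP 4.3 defines four seizure rates. The numerators are seizures recorded in the caregiver diary. The denominators are:

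- Baseline monthly: "screening/baseline duration in months ([first dose date screening date] divided by 30.4375".
- Baseline weekly: "screening/baseline duration in weeks ([first dose date screening date] divided by 7".
- On-treatment monthly: "treatment duration in months (treatment duration divided by 30.4375".
- On-treatment weekly: "treatment duration in weeks (treatment duration ([first dose date screening date] divided by 7".

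A minus sign is evidently meant between the two dates; its absence here is a text-conversion matter and no part of the point. The same section sets the length of treatment: "Treatment duration in days will be derived as follows: Date of Last Dose Date of First Dose + 1", again with a minus sign intended.

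SAP 6.9 relies on these definitions: "Evaluation of total, monthly, and weekly seizure frequency will be derived as defined in Section 4.3". Its next paragraph names total and monthly seizures, but not weekly, for the summary of observed values and change from baseline, and applies a Wilcoxon signed rank test to within-subject changes.

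On the source data, Protocol 9.5.10 says "A Caregiver Diary will be completed daily by the caregiver". The diary footnote to Protocol Table 1 lists a daily summary log and a seizure log as separate parts. SAP 4.2.3 rules out imputing missing safety data. Neither document says how a day with no diary record enters a seizure rate.

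**The concern.** Three of the four formulas divide by the length of their own period. The fourth names treatment duration in words but carries the bracket from the baseline weekly formula, and its parentheses do not close. It cannot be programmed as it stands. A programmer who follows the bracket would divide seizures from about 13 weeks of treatment by 4 to 6 weeks of screening, and a child with a constant rate would appear to worsen sharply.

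The second issue is quieter but reaches the monthly rate, which SAP 6.9 does display. A day with no diary record adds one day to the denominator and nothing to the numerator, so it is scored as seizure-free. If the share of such days differs between screening and treatment, the within-subject change is distorted. There is no control arm against which such a distortion would cancel, and seizures are reported in the safety section.

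**Working it through.** The plan states no seizure rate, so there is no figure to reproduce. The check applies the SAP 4.3 formulas to a child whose true rate does not change.

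**Inputs**
- Screening length S = 28 to 42 days (4 to 6 weeks; Protocol 9.1).
- Treatment duration T = 91 days (Protocol 9.4.2).
- Assumed for illustration: a constant 1 seizure per week, so 13 seizures on treatment.

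**1. On-treatment weekly formula**

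| Denominator | S = 28 | S = 42 |
|---|---|---|
| T / 7 (words of the sentence) | 13 / 13 = 1.00 per week | 13 / 13 = 1.00 per week |
| S / 7 (bracket) | 13 / 4 = 3.25 per week | 13 / 6 = 2.17 per week |
| Inflation, T / S | 91 / 28 = 3.25 | 91 / 42 = 2.17 |

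The factor does not depend on the assumed rate. By the bracket, a true halving would read as 0.5 x 3.25 - 1 = +62.5% or 0.5 x 2.17 - 1 = +8.3%.

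Cross-check against the adjacent formula: the monthly rate is 13 / (91 / 30.4375) = 4.35. For one period, monthly over weekly must equal 30.4375 / 7 = 4.35. The denominator T / 7 gives 4.35 / 1.00 = 4.35, as it should. The bracket gives 4.35 / 3.25 = 1.34 or 4.35 / 2.17 = 2.01.

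Reading the expression as a product does not rescue it: 91 x 28 / 7 = 364 and 91 x 42 / 7 = 546, neither of which is a number of weeks.

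**2. Calendar-day denominators**

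Let c be the share of days in a period that have a diary record, and suppose seizures on the other days go unrecorded. The calculated rate is then the true rate x c. For an unchanged true rate, the apparent change is c(treatment) / c(screening) - 1. The documents give no completeness figures, so every value below is an assumption.

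| Screening | Treatment | Apparent change |
|---|---|---|
| 95% | 85% | 0.85 / 0.95 - 1 = -10.5% |
| 95% | 70% | 0.70 / 0.95 - 1 = -26.3% |
| 90% | 90% | 0 |
| 80% | 100% | 1.00 / 0.80 - 1 = +25% |

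Dividing by days with a record removes c from both rates and returns a change of 0 in every row, provided the blank days are missing at random.

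**The case against.** **On the weekly formula.** The intended meaning is plain. The sentence itself says treatment duration in weeks, that duration is defined in the same section, and the monthly formula beside it is right. SAP 4 also requires independent validation of the programs. All of this stands and makes the slip easy to correct, but it does not make the written rule usable: validation checks consistency with the plan, and here the plan is inconsistent with itself. A reader might infer that the trial's displayed seizure results will show a false rise. The documents do not support that, because the display sentence in SAP 6.9 leaves out the weekly rate. What is exposed is the derived weekly variable and any listing or table built on it.

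**On diary days.** A reader might infer that diary keeping wanes over 13 weeks, so the plan would manufacture a fall in seizures. The documents do not support that direction. In screening the diary is reviewed at Visits 1, 2 and 3, with 2 to 4 weeks between the last two. On treatment it is reviewed at every visit, which is weekly. Completeness could be better on treatment, and the error would then be a false rise. Close review may also keep gaps small in both periods.

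It is also fair to say that a seizure log filled in only when a seizure occurs is properly empty on a quiet day. That bears on the remedy: completed days must come from the daily summary log, since counting days with a seizure-log entry would grossly inflate the rate. It does not settle what happens on days when nothing was recorded at all.

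Finally, the stakes are bounded. SAP 7.5 treats all significance levels as nominal, and SAP 7.1 does not list seizure rate as an efficacy variable.

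**Conclusion.** The weekly formula is wrong as written. Taken by its bracket, it inflates the on-treatment weekly rate 2.17-fold to 3.25-fold for a child who completes 91 days after a 42-day to 28-day screening period. It is one formula of four, with an evident intended reading, and the weekly rate is derived but not named for display. It should be corrected, but it does not undermine the displayed monthly comparison.

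The calendar-day denominator is an unstated rule for missing diary days that reaches all four rates, including the monthly one. Its bias has no known sign or size: zero if completeness is equal in the two periods, a false fall if it is worse on treatment, a false rise if it is worse in screening. The illustrated range of -26.3% to +25% rests wholly on assumed completeness. The documents support stating the rule and reporting completeness; they do not support a prediction that seizures will appear to fall.

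**What to change.** 1. In SAP 4.3, write the on-treatment weekly denominator as treatment duration / 7 and delete the screening bracket. This costs nothing.
2. In SAP 4.3, state how days without a diary record are treated. Where the daily summary log identifies completed days, define the rate in both periods as seizures recorded / completed diary days, x 7 for weekly or x 30.4375 for monthly. Alternatively, keep the calendar-day rate and give this one beside it as a sensitivity analysis.
3. Report the number and percent of completed diary days per period next to the rates.

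Items 2 and 3 need one derived count per child and period. The documents do not show whether daily completion is held in the database for screening, so that should be confirmed first. The downsides are slightly less precision for a child with few completed days, and an assumption that blank days are missing at random: if caregivers tend to skip quiet days, the completed-day rate is too high. Under SAP 4, changes made before database lock remain a priori; later ones would be post hoc.
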